### **7.3 PLANNED ANALYSES**

The efficacy analysis will be based on the randomised set (RS), including all randomised patients.

The safety analysis will be based on the treated set (TS), which consists of all patients treated with at least one dose of the trial medication.

For both efficacy and safety analyses, treatment will be evaluated as randomised.

For serum creatinine and values based on upon this measurement such as eGFR, baseline will be defined as the mean of all available measurements from the screening visit until start of randomised trial medication.

For all other endpoints, baseline will be defined as the last available measurement before start of randomised trial medication.

Note that for the primary endpoint the higher measurement for each day is selected as the test result for that day. Therefore the last available measurement before start of trial medication will refer to the higher value on the day of the last measurement before treatment intake.

#### **7.3.1 Primary endpoint analyses**

The primary endpoint ‘change from baseline to week 12 in exercise capacity’ will be evaluated using a normal approximation of the Wilcoxon rank test using the randomized set. For estimation of effect the non-parametric Hodges-Lehmann estimate for the median difference will be calculated. Any confirmatory conclusion such as for hierarchical testing

will be based on the result of the Wilcoxon rank test and will not consider the Hodges-Lehmann estimate or the corresponding confidence interval, which are given to support interpretation.

If repeated distance walked in 6 minutes (6MWT) measurements on the same day are available the longest distance will be used for this day.

Change from baseline will be defined as distance walked in 6 minutes (6MWT) at week 12 assessment minus the distance walked at baseline.

If no value for the 6MWT is available at week 12, an imputed value as defined in [table 7.5: 1](#) will be used.

Sensitivity analysis for the primary endpoint will include using a mixed model repeated measure analysis (MMRM) with baseline 6MWT as a covariate without imputation of missing values.

### 7.3.2 Secondary endpoint analyses

#### Key secondary endpoints

Both key secondary endpoints ‘Change from baseline to week 12 in heart failure symptoms as measured by the KCCQ TSS’ and ‘Change from baseline to week 12 in CHQ-SAS dyspnea score’ will be evaluated using a normal approximation of the Wilcoxon rank test using the randomized set. For estimation of effect the non-parametric Hodges-Lehmann estimate for the median difference will be calculated.

Change from baseline in both scores will be defined as the endpoint value at week 12 minus the last available endpoint value before start of randomised trial medication.

If no questionnaire is available at week 12, an imputed value as defined similar to the imputation for the primary endpoint will be used.

Sensitivity analysis for the key secondary endpoint will include using a mixed model repeated measure analysis with baseline of the key secondary endpoint as a covariate without imputation of missing values.

#### Other secondary endpoints

Change from baseline to week 6 in exercise capacity as measured by the distance walked in 6 minutes will be evaluated using the same model as for the primary endpoint.

Change from baseline of Clinical Congestion Score at week 12 will be evaluated using an mixed model repeated measure analysis (MMRM) analysis over time. The model will include the factor treatment and the linear covariate of baseline Clinical Congestion Score.

Proportion of patients in every category of global impression of change at week 12 will be evaluated using Cochran-Mantel-Haenszel test. Details on combining categories if the proportion of patients in one of the categories is small will be given in the TSAP.

Proportions of patients categorized by the shift in scores between baseline and week 12 in patient global impression of severity score will be evaluated using Cochran-Mantel-Haenszel test. Details on combining categories if the proportion of patients in one of the categories is small will be given in the TSAP.

The endpoint “Change from baseline in NT-proBNP at week 12” (after log-transformation) will be evaluated using a MMRM analysis over time with baseline log-transformed NT-proBNP as a covariate without imputation of missing values.

### 7.3.3 Further endpoint analyses

Endpoints describing responders such as increase in 6MWT  $\geq 30$  m or response in KCCQ or CHQ domains will be evaluated using a Chi-Square test.

Proportions of patients categorized by the shift in scores between baseline and week 6 in patient global impression of severity score will be evaluated using Cochran-Mantel-Haenszel test. Details on combining categories if the proportion of patients in one of the categories is small will be given in the TSAP.

Proportion of patients in every category of patient global impression of change at week 6 will be evaluated using Cochran-Mantel-Haenszel test. Details on combining categories if the proportion of patients in one of the categories is small will be given in the TSAP.

Proportion of patients in every category in clinician global impression of change at week 6 and week 12 will be evaluated using Cochran-Mantel-Haenszel test. Details on combining categories if the proportion of patients in one of the categories is small will be given in the TSAP.

Proportions of patients categorized by the shift in scores between baseline and week 6 (week 12) in clinician global impression of severity score will be evaluated using Cochran-Mantel-Haenszel test. Details on combining categories if the proportion of patients in one of the categories is small will be given in the TSAP.

Change from baseline continuous endpoints such as KCCQ domains or CHQ domains at week 6 and Week 12 will be evaluated using a MMRM analysis over time. The model will include treatment as fixed categorical effect and baseline of the respective endpoint as fixed continuous effect.

Change from baseline in Clinical Congestion Score at week 6 will be evaluated by the same MMRM used to evaluate Clinical Congestion Score at week 12 described for the secondary endpoint.

Change from baseline in NT-proBNP at week 6 will be evaluated by the same MMRM used to evaluate NT-proBNP at week 12 described for the secondary endpoint.

Proportions of patients categorized by the shift in scores between baseline and week 12 in NYHA class will be evaluated using Cochran-Mantel-Haenszel test. Details on combining categories if the proportion of patients in one of the categories is small will be given in the TSAP.

Change from baseline to week 12 in patient-rated assessment of dyspnea and fatigue by the Borg scale as part of the 6MWT will be presented descriptively.

Other further endpoints will be analysed descriptively.

#### **7.3.4 Safety analyses**

Adverse events will be coded using the Medical Dictionary for Drug Regulatory Activities (MedDRA). Standard BI summary tables and listings will be produced. All adverse events with an onset between start of treatment and end of the residual effect period (REP), a period of 7 days after the last dose of trial medication, will be assigned to the on-treatment period for evaluation.

All treated patients will be included in the safety analysis. In general, safety analyses will be descriptive in nature and will be based on BI standards. No hypothesis testing is planned.

Statistical analysis and reporting of adverse events will concentrate on treatment-emergent adverse events, i.e. all adverse events occurring between start of treatment and end of the residual effect period. Adverse events that start before first drug intake and deteriorate under treatment will also be considered as 'treatment-emergent'.

Frequency, severity, and causal relationship of adverse events will be tabulated by system organ class and preferred term after coding according to the current version of the Medical Dictionary for Drug Regulatory Activities (MedDRA) at the database lock.

Laboratory data will be analysed both quantitatively as well as qualitatively. The latter will be done via comparison of laboratory data to their reference ranges. Values outside the reference range as well as values defined as clinically relevant will be summarised. Treatment groups will be compared descriptively with regard to distribution parameters as well as with regard to frequency and percentage of patients with abnormal values or clinically relevant abnormal values.

Vital signs, physical examinations, or other safety-relevant data observed at screening, baseline, during the course of the trial and at the end-of-trial evaluation will be assessed with regard to possible changes compared to findings before start of treatment.

Reasons for discontinuation and use of post-baseline concomitant medications will be tabulated.

The details of the analysis will be specified in the TSAP.

### 7.3.5 Pharmacokinetic and pharmacodynamic analyses

Not applicable.

## 7.4 INTERIM ANALYSES

No interim analysis is planned but a DMC will be in place with tasks as described in [Section 8.7](#).

## 7.5 HANDLING OF MISSING DATA

Patients with an available week 12 measurement of the 6MWT, regardless of whether on or off-treatment, will be ranked based on change from baseline in 6MWT distance at week 12.

If a patient performs the visit at week 12 but is unable to walk or unable to perform the 6MWT due to safety concerns, then this will be noted accordingly in the case report form and will not be regarded as missing data. This case will be evaluated as a measured distance of 0m.

Missing data will be imputed according to the rules outlined in [table 7.5: 1](#), and ranks will be assigned based on the imputed data. Imputed data will also be used to calculate the Hodge Lehmann estimates for the median difference. Note that no imputation will be used in the MMRM analysis that serves as sensitivity analysis in this trial.

All imputed data due to missing data will be lower than measured values. The lowest measurable value of the primary endpoint of change from baseline in 6MWT distance is a reduction by 350m, i.e. the highest possible baseline value (350 m), and at week 12 the lowest possible value of 0m. Therefore, all imputed values for change from baseline for patients with missing walking distance at week 12 are below -350 m.

Table 7.5: 1 Imputation rules for missing primary endpoint

	Category	Ranking	Case description	Imputed change from baseline in 6MWT for described case (in m)*
1	Missing data on 6MWT at week 12 and no clinical event: Patients with missing 6MWT at week 12 and no event as in category 2 or 3	If post-baseline value is available, rank by last available value. Rank below if no post-baseline value is available	Patient has a change from baseline to last available value of x m, no clinical event	-352 +x/1000
			No information of post-baseline 6MWT distance and no clinical event	-354
2	Missing data and clinical event (except death). A clinical event is defined as ongoing SAE or AE leading to treatment discontinuation and patient is alive at week 12	Ranked above patients who died, but below patients with missing data and no clinical event.	Patient has ongoing SAE or AE leading to treatment discontinuation, no information of week 12 6MWT distance and patient alive at week 12.	-356
3	Patient died before the measurement of 6MWT at week 12 was conducted.	Ranked by time to death from randomization	Patient died y days after randomization	-358+y/1000

Similar rules following the same strategy will be defined in the TSAP to impute missing values for the key secondary endpoints.

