## 6.2 IMPORTANT PROTOCOL DEVIATIONS

A protocol deviation (PD) is important, if it affects the rights or safety of the study patients or if it can potentially influence the primary outcome measures for the respective patients in a way that is neither negligible nor in accordance with the study objectives.

Important protocol deviations (iPDs) will be described in the clinical trial report (CTR). A listing of patients with medication code broken will be provided.

Table 6.2: 1 Important protocol deviations

Category / Code	Description	Requirements	Excluded from
A	Entrance criteria not met		
A1	Target indication not met		
A1.06	No chronic HF or no NYHA class II-IV	Inclusion criterion #5 not met	None
A1.07	Conditions on ejection fraction (EF) not met	Inclusion criterion #6 not met	None
A1.08	Conditions on NT-proBNP not met	Inclusion criterion #7 not met	None

Table 6.2: 1 Important protocol deviations (cont.)

Category / Code	Description	Requirements	Excluded from
A2/3	Other entrance criteria not met		
A2.02	Age out of range	Inclusion criterion #1 not met	None
A2.08	Specific inclusion criterion for women of child-bearing potential not met	Inclusion criterion #2 not met	None
A2.14	6MWT distance above 350m at screening or baseline or below 100m at baseline	Inclusion criterion #4 or exclusion criterion #10 not met	SensRS1
A2.12	Inclusion criterion on stable concomitant medication not met	Inclusion criterion #8 not met	None
A2.13	Use of medical devices not appropriate or device implanted recently or intent to implant	Inclusion criterion #10 or exclusion criterion #18 not met	None
A3.44	Patient with unstable conditions	Exclusion criteria #1, #2, #6, #9, #13, #17, #20, #21 or #25 not met, inclusion criterion #9 not met	None
A3.49	Participation in another Empagliflozin HF trial	Exclusion criterion #3 not met	None
A3.51	Type 1 diabetes	Exclusion criterion #4 not met	None
A3.09	Renal insufficiency or renal impairment (assessed by eGFR)	Exclusion criterion #5 not met	None
A3.33	Systolic blood pressure at visit 1 or 2 out of range	Exclusion criterion #7 not met	None
A3.31	Atrial fibrillation or atrial flutter with a resting heart rate >110bpm	Exclusion criterion #8 not met	None
A3.48	Presence of condition that precludes exercise testing	Exclusion criterion #11 not met	None
A3.47	Participation in structured Exercise training	Exclusion criterion #12 not met	None

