### **6.3 SUBJECT SETS ANALYSED**

The following patient sets are defined in section 7.3 of the protocol:

- **Randomised set (RS)**  
This patient set includes all randomised patients, whether treated or not. Treatment will be evaluated as randomised.
- **Treated set (TS)**  
This patient set includes all patients who were dispensed study medication and were documented to have taken at least one dose of investigational treatment. Treatment will be evaluated as randomised.

In addition the following patient set is defined:

- **Screened Set (SCR)**  
Consists of all patients screened for the trial, with informed consent given and who completed at least one screening procedure at Visit 1.

For sensitivity analyses the following patients set is defined:

- **Sensitivity analysis set 1 (SensRS1)**  
Randomised patients excluding patients with an iPD related to 6MWT, i.e. iPD categories A2.14, G3.48 and G3.49 of [Table 6.2: 1](#)
- **Sensitivity analysis set 2 (SensRS2)**  
Randomised patients excluding patients for which at least one on-treatment value of urine glucose test result was included in the safety laboratory reports posted to a portal by the central laboratory, and the reports were accessed before database lock.
- **Sensitivity analysis set 3 (SensRS3)**  
Randomised patients excluding non-diabetic patients for which at least one on-treatment value of urine glucose test result was included in the reports posted and accessed before database lock.

Demographics and baseline characteristics as well as the efficacy analysis will be based on the RS. Demographics will be repeated on the TS if the number of patients in the analysis sets differ by more than 5%. The safety analysis will be based on the TS.

Overall number of patients participating in the study (screened, randomised, screened but not randomised, etc.) by region and country will be based on the SCR.

Table 6.3: 1 Subject sets analysed

Class of endpoint	Subject set		
	Screened Set	Randomised set	Treated set
Primary and key secondary endpoints		X	X
(other) Secondary and further endpoints		X	
Safety endpoints			X
Demographic/baseline endpoints		X	X 
Extent of exposure			X
Disposition	X		

 Demographics will be repeated on the TS if the number of patients in the analysis sets differ by more than 5%.

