### 6.6.3 Secondary endpoints

Handling of missing data for the change from baseline to week 6 in exercise capacity as measured by the distance walked in 6 minutes will be analogous to the primary endpoint, see [Table 6.6.3:1](#)

Table 6.6.3: 1 Imputation rules for missing exercise capacity at week 6

	Category	Ranking	Case description	Imputed change from baseline in 6MWT for described case (in m)*
1	Missing data on 6MWT at week 6 and no clinical event: Patients with missing 6MWT at week 6 and no event as in category 2 or 3	Ranked above patients who died or patients with a clinical event, but below patients with available measurement at week 6.	No information of post-baseline 6MWT distance and no clinical event	-354
2	Missing data and clinical event (except death). A clinical event is defined as ongoing SAE or AE leading to treatment discontinuation and patient is alive at week 6	Ranked above patients who died, but below patients with missing data and no clinical event.	Patient has ongoing SAE or AE leading to treatment discontinuation, no information of week 6 6MWT distance and patient alive at week 6.	-356
3	Patient died before the measurement of 6MWT at week 6 was conducted.	Ranked by time to death from randomisation	Patient died y days after randomisation	$-358+y/1000$

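### The imputed 6MWT changes begin at about −352 m, so a patient randomised above 350 m with a measured fall of 352 m or more can rank below missing patients, and from 358 m below deaths

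*Protocol*

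**What the plan says.** Protocol 7.5 sets the principle: "All imputed data due to missing data will be lower than measured values". Its reason is that the lowest measurable change "is a reduction by 350m, i.e. the highest possible baseline value (350 m), and at week 12 the lowest possible value of 0m". Table 7.5:1 then gives four fixed values for the change from baseline:

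- Category 1, no clinical event, with a post-baseline test showing a change of x m: −352+x/1000.
- Category 1, "No information of post-baseline 6MWT distance and no clinical event": −354.
- Category 2, ongoing SAE or AE leading to discontinuation, alive at week 12: −356.
- Category 3, death y days after randomisation: −358+y/1000.

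The numbers decide the order: "and ranks will be assigned based on the imputed data". They also enter the Hodges-Lehmann estimate. A patient who attends week 12 but cannot walk is not missing and counts as a measured 0 m. SAP 6.6 words this more broadly, covering any attended visit at which the test was not done.

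SAP Table 6.2:1 lists, as important deviation A2.14, "6MWT distance above 350m at screening or baseline or below 100m at baseline". SAP 6.3 removes these patients from SensRS1 only. Of the randomised set it says "This patient set includes all randomised patients, whether treated or not", and SAP 7.4.1 runs the primary analysis on all randomised patients. SAP 6.6.1 adopts protocol 7.5 without capping baseline or changing the values. The week 6 table ("Imputation rules for missing exercise capacity at week 6") reuses −354, −356 and −358+y/1000.

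**The concern.** The 350 m limit is an entry criterion, not a bound of the measurement. The imputed values sit only 2 to 8 m below −350 m. A patient randomised in breach of the criterion who then cannot walk at week 12 has a measured change equal to minus the baseline, and this can fall among or below the imputed values. The primary ranking would then place a living patient who attended week 12 below patients with no data, or below patients who died. Protocol 7.5 and SAP 6.6 both state the opposite order.

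The questionnaire endpoints do not share the problem. Their imputed values lie below true scale limits (changes of −100 for KCCQ-TSS and −6 for CHQ-SAS dyspnea), so no measured value can reach them.

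**Working it through.** **The plan's own figures (protocol 7.7).** Inputs: difference 30 m, SD 72 m, two-sided 0.05, 90% power, 1:1 allocation.

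- p = P(X<Y) = Φ(−30/(72·√2)) = 0.384.
- n per group = (1.960+1.282)²/(6·(p−0.5)²), which rounds up to 131. For 40 m and 50 m, with p unrounded, it gives 76 and 50. All three match Table 7.7:1.
- Simulated power at 150 per group with 5%, 8% and 10% imputed to the bottom is 90.5%, 87.6% and 85.4% (20,000 runs). Table 7.7:2 gives 90%, 87% and 85%.

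The sample size therefore reproduces and is not in question.

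**Where the order fails.** With 0 m at week 12, change = −baseline. Distances are recorded in whole metres (protocol 10.1.4). For deaths on days 1 to 92, category 3 runs from −357.999 to −357.908.

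| Baseline (m) | Change (m) | Ranks below |
|---|---|---|
| 350, 351 | −350, −351 | no imputed patient |
| 352 | −352 | category 1 with x > 0 (tie at x = 0) |
| 353, 354 | −353, −354 | all category 1 with a post-baseline test (354 ties with −354) |
| 355, 356 | −355, −356 | all category 1 (356 ties with −356) |
| 357 | −357 | also category 2 |
| 358 or more | −358 or lower | also every death, since −358 < −358+y/1000 for y ≥ 1 |

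The same follows from any measured fall of that size, not only from 0 m: 420 m falling to 50 m gives −370. At week 6 the table has no −352 row, so failure starts at 355 m.

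**Effect on the test.** The null standard error of the rank sum at 150 per group is √(150·150·301/12) = 751.25. A misplaced patient changes the rank sum only by the number of imputed patients in the other arm that it wrongly passes. With 5% missing that is 7 or 8, so the shift in Z is at most 8/751.25 = 0.011. With 10% missing it is 15/751.25 = 0.020.

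A simulation compared the plan's values with values set below all measured data. It assumed 5% missing per arm and k patients, all on empagliflozin, with a measured fall of 360 to 400 m.

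| k | Power, plan's values | Power, corrected values | Runs with a changed decision |
|---|---|---|---|
| 1 | 87.8% | 87.9% | 0.2% |
| 2 | 85.1% | 85.6% | 0.5% |
| 3 | 81.8% | 82.6% | 0.8% |
| 5 | 73.1% | 74.9% | 1.7% |

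The fall in power down the table comes from giving one arm k very poor outcomes. Only the difference between the two power columns is due to the coding.

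**How many patients.** The documents give no count of patients randomised above 350 m. As an assumption, take 2% of 300 = 6 with baseline above 352 m, and 3% to 5% of patients scored 0 m. Then 6 × 0.03 = 0.18 to 6 × 0.05 = 0.30 patients are expected.

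**The case against.** The strongest reply has four parts.

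- **The order is already stated in words.** SAP 6.6 says that imputed data lie below measured data and that death ranks lowest. The residual-rank analysis in SAP 7.4.2 places patients without week 12 data below all others, which is ranking by category. This shows the intent is clear. It does not remove the mismatch, because SAP 6.6.1 and 7.4.1 send the programmer back to the numbers in protocol 7.5.
- **The case is rare.** Table 6.2:1 codes nearly every entry criterion, and A2.14 pools three situations, of which only a baseline above 350 m matters here. Any test above 350 m at Visit 1 or 2 is a screen failure, so a breach must be combined with an almost total loss of walking distance. This stands.
- **A check exists.** SAP 7.4.2 repeats the primary analysis on SensRS1, which excludes A2.14 patients, and the MMRM uses no imputation. The Hodges-Lehmann estimate carries no confirmatory weight, and week 6 is outside the testing hierarchy. This stands too.
- **A table note may be missing.** The value columns of protocol Table 7.5:1 and SAP Table 6.6.3:1 carry an asterisk whose note is not in the text available here. A note capping baseline at 350 m would settle the matter.

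A reader might infer that every patient randomised above 350 m who scores 0 m is misranked. The table above does not support that: 351 m is safe, and so is a distance above 350 m at screening with a baseline at or below it. Nor do the figures support a reading that the primary test or its power is compromised.

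**Conclusion.** The point holds as a mismatch between numeric coding and stated order. For a measured change of −352 m or lower, the fixed values contradict the ordering in protocol 7.5 and SAP 6.6. The failure starts with some category 1 patients at 352 m and reaches deaths at 358 m. The SAP itself provides for the deviation that makes this possible and keeps the patient in the confirmatory analysis.

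The effect on the p-value is very small: about 0.01 in Z per affected patient at 5% missing, with well under one such patient expected on the assumed rates. The SensRS1 analysis would show any influence. The effect on the Hodges-Lehmann estimate was not quantified. The conclusion assumes that no table note caps baseline at 350 m.

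**What to change.** In SAP 6.6.1 and Table 6.6.3:1, do one of the following:

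- Rank by category first: all measured changes, then categories 1, 2 and 3, keeping the order within each.
- Set the imputed values below any attainable measured change, for example by subtracting a further 1000 m: −1352+x/1000, −1354, −1356 and −1358+y/1000. At week 6 use the last three.

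A fall of 1352 m would need a baseline of at least 1352 m in six minutes, or 13.5 km/h, so the second option cannot fail in a walk test. It also keeps one set of numbers for both the ranks and the Hodges-Lehmann estimate.

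Because the values stand in protocol Table 7.5:1, list the change in SAP 4.1 and point SAP 7.4.1 to the revised rule. The cost is a short SAP revision, best made before unblinding. No rank that already follows the stated order changes, and the sample size is unaffected.
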